## 6.11. Safety Analyses

Unless specified otherwise, safety analyses outlined in the following subsections will be conducted for the safety population.

The safety and tolerability of treatment will be assessed by summarizing

- TEAEs
  - by PT
  - by PT nested within SOC
  - by maximum severity
  - by investigator classification of related to study treatment
- serious adverse events (SAEs) by PT
- AEs leading to discontinuation by PT, and
- vital signs.

Baseline for all safety measures includes all data prior to injection of study treatment. Postbaseline includes all data in Study Period II from injection of study treatment to completion of Study Period II.

For safety categorical variables and categorical variables of demographics and baseline characteristics, comparisons between treatment groups will be performed using Fisher's exact test. For continuous variables of demographics and baseline characteristics, an analysis of variance (ANOVA) with treatment as an independent variable in the model will be performed.

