WMC administration		X ^a		X		
 • Fasting is defined as no food or drink, except water, for at least 8 hours prior to testing. • No alcohol consumption for 24 hours prior to ingesting the WMC and 6 hours after ingestion. • Tobacco use should also be avoided for 8 hours before ingestion and 6 hours after ingestion of the WMC. • Patients will consume a SmartBar immediately before ingesting WMC and will fast for 6 hours following WMC ingestion. • Patients should not sleep for 6 hours after ingesting the WMC.
Assessment that WMC has been expelled			X ^b	X ^b		The recorder will be returned to the site and data will be uploaded and evaluated to confirm WMC expulsion at Visit 3 and between Visits 4 and 5.
Study treatment administered			X			
Procedures						
Informed consent	X					
Inclusion and exclusion criteria	X					
Concomitant medication review	X	X	X	X	X	

Study Period	SP I Screening and Baseline GI Transit Time		SP II Single-Blind Treatment and Post WMC Evaluation			Notes
	V1	V2	V3	V4	V5	
Urine pregnancy test, performed locally	X				X	
Eligible patient randomized via IWRS			X			
Physical examination	X					
Height	X					
Weight	X					
Medical history	X					
Substance use	X		X	X		Substances: alcohol, caffeine, nicotine, tobacco.
Vital signs	X		X	X	X	Includes body temperature, sitting blood pressure, and pulse.
Assessment of migraine and headache days	X					Will be done retrospectively for the previous month.
GI Symptom Rating Scale (GSRS)	X		X	X	X	
Bristol Stool Form Scale	X		X	X	X	
Spontaneous Bowel movement (SBM) frequency evaluation	X		X	X	X	
Adverse events	X	X	X	X	X	

Abbreviations: GI = gastrointestinal; IBS = irritable bowel syndrome; IWRS = interactive web-response system; SP = study period; TT = transit time; V = visit; WMC = wireless motility capsule.

- ^a If the patient meets the requirement of fasting at Visit 1, then Visit 1 and Visit 2 could be combined. Sites must not instruct patients to fast prior to signing the ICF
- ^b An x-ray may be obtained in the event that the expulsion of the WMC cannot be confirmed.

3. Introduction

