Erenumab is a human monoclonal antibody that antagonizes the CGRP receptor. The efficacy of erenumab for the prevention of migraine has been demonstrated in three Phase 3 randomized, double-blind trials (Goadsby et al. 2017; Tepper et al. 2017; Dodick et al. 2018). Erenumab 70 and 140 mg were both found to be effective in reducing the number of monthly migraine days in patients with episodic and chronic migraine. No serious safety concerns were identified with a clear causal relationship to erenumab. The incidences of SAEs and discontinuations due to AEs were low, and the most common adverse reactions (with an incidence of at least 2% for either dose of erenumab and at least 2% greater than placebo) were injection site reactions, constipation, and cramps/muscle spasms (Ashina et al. 2019; Aimovig package insert, 2020). Hypersensitivity reactions (including rash, angioedema, and anaphylaxis), constipation with serious complications, and new-onset or worsening of pre-existing hypertension have been reported with erenumab in postmarketing experience.

The risks of WMC include capsule retention and aspiration, which rarely and very rarely are reported. With regard to the cases of capsule retention, they resolved either without intervention or with endoscopy/colonoscopy. Surgery was required for resolution in one instance of capsule small bowel retention that led to identification of a stricture.

To minimize these risks, patients with a history of GI surgery, a self-reported history of gastric bezoars, swallowing disorders, severe dysphagia to food or pills, suspected or known strictures, fistulas, or physiological/mechanical GI obstruction are excluded to participate in the study.

Patients should not undergo a magnetic resonance imaging (MRI) test until capsule passage is confirmed by review of the MotiliGI™ graph or x-ray of kidneys, ureter, and bladder. If a WMC is in the body during an MRI test, there is a risk of damage to the GI tract.

4. Objectives and Endpoints

Table CGBC.4.1 shows the objectives and endpoints of the study.

Table CGBC.4.1. Objectives and Endpoints

Objectives	Endpoints

Primary Objective To evaluate colonic transit time (CTT) in patients with migraine 1 week prior to and 2 weeks after administration of an initial loading dose of galcanezumab 240 mg or erenumab 140 mg.
	Change from baseline in CTT after administration of galcanezumab or erenumab within each treatment group in hours at the end of Week 2.

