9.2. Adverse Events

Investigators are responsible for monitoring the safety of patients who have entered this study and for alerting Lilly or its designee to any event that seems unusual, even if this event may be considered an unanticipated benefit to the patient.

The investigator is responsible for the appropriate medical care of patients during the study.

Investigators must document their review of each laboratory safety report.

The investigator remains responsible for following, through an appropriate health care option, AEs that are serious or otherwise medically important, considered related to the study treatment or the study, or that caused the patient to discontinue the study treatment before completing the study. The patient should be followed up until the event resolves, stabilizes with appropriate diagnostic evaluation, or is reasonably explained. The frequency of follow-up evaluations of the AE is left to the discretion of the investigator.

Lack of drug effect is not an AE in clinical studies, because the purpose of the clinical study is to establish treatment effect.

The investigator will record all relevant AE and SAE information in the eCRF. After the ICF is signed, study site personnel will record via eCRF the occurrence and nature of each patient's preexisting conditions, including clinically significant signs and symptoms of the disease under treatment in the study. In addition, site personnel will record any change in the condition(s) and any new conditions as AEs. Investigators should record their assessment of the potential relatedness of each AE to protocol procedure and study treatment, via eCRF.

The investigator will interpret and document whether or not an AE has a reasonable possibility of being related to study treatment, study device, or a study procedure, taking into account the disease, concomitant treatment, or pathologies.

A "reasonable possibility" means that there is a cause-and-effect relationship between the study treatment, study device, and/or study procedure and the AE.

The investigator answers yes/no when making this assessment.

Planned surgeries and nonsurgical interventions should not be reported as AEs unless the underlying medical condition has worsened during the course of the study.

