10.1. Sample Size Determination

Assuming within-group mean difference in CTT is about 4.2 hours with standard deviation of approximately 8, a sample of 30 patients in each treatment group will provide 80% power to detect the difference within the treatment group. The total sample size for the study would be 60.

Assuming 20% screen failure rate, approximately 75 patients may be screened to enroll 60 patients into the study. Eligible patients will be randomized in a 1:1 ratio to galcanezumab or erenumab to have about 30 patients in each treatment group.

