10.3.4. Safety Analyses

The safety analyses will be conducted for the single-blind treatment phase.

Safety data will be summarized by treatment group.

The safety and tolerability of treatment will be assessed by summarizing adverse events:

- TEAEs
 - by Preferred Term (PT)
 - by System Organ Class (SOC)
 - by maximum severity
 - considered to be related to study treatment by investigator
- SAEs, and
- AEs leading to discontinuation.

Treatment-emergent adverse events are defined as the reported AEs that first occurred or worsened during the postbaseline phase compared with baseline phase. For each TEAE, the severity level of the event (mild, moderate, or severe) will be determined by patient or physician opinion. The Medical Dictionary for Regulatory Activities (MedDRA) Lowest Level Term will be used in the treatment-emergent computation. For each Lowest Level Term, the maximum severity at baseline will be used as the baseline severity. If the maximum severity during postbaseline is greater than the maximum baseline severity, the event is considered to be treatment emergent for the specific postbaseline period. For each patient and TEAE, the maximum severity for the MedDRA level being displayed (PT, High Level Term, or SOC) is the maximum postbaseline severity observed from all associated Lowest Level Terms mapping to that MedDRA level.

For events that are gender specific, the denominator and computation of the percentage will include only patients from the given gender.

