### 6.8. Patient Characteristics

The following patient characteristics at baseline will be summarized by treatment group for the ITT population:

- demographics (age, gender, ethnic origin, height, weight, and BMI)
- medical history and preexisting conditions
- total gut and segmental transit times
- GI symptom rating scale, SBM frequency, and BSFS, and
- alcohol, tobacco, caffeine, and nicotine consumption.

Medical history and preexisting conditions will be summarized by descending frequency of Preferred Term (PT) nested within System Organ Class (SOC). Medical history is defined as illness(es) that ended prior to the signing of informed consent. Preexisting conditions and adverse events (AEs) at baseline are those AEs occurring during the baseline/screening visits for the study period.

The percentage of patients who report a change in alcohol, tobacco, caffeine, or nicotine consumption during the study will be summarized.

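### The SAP does not attribute capsule adverse events to the device or procedure, reports no expulsion outcome, and can leave non-serious first-capsule events only in the baseline summary

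*SAP*

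**What the plan says.** Protocol 3.3 identifies the capsule's own hazards: "The risks of WMC include capsule retention and aspiration, which rarely and very rarely are reported". Two provisions gather information on them. Under the Schedule of Activities (Protocol Section 2) the recorder is returned and "data will be uploaded and evaluated to confirm WMC expulsion at Visit 3 and between Visits 4 and 5", with an optional x-ray where passage cannot be confirmed. Under Protocol 9.2 the investigator judges "whether or not an AE has a reasonable possibility of being related to study treatment, study device, or a study procedure". The eCRF instruction in that section expressly covers relatedness to procedure and to treatment.

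The analysis plan uses little of this. In SAP 6.11 the single relatedness breakdown of treatment-emergent events is "by investigator classification of related to study treatment". Protocol 10.3.4 has the same breakdown and says "The safety analyses will be conducted for the single-blind treatment phase". SAP 6.11 counts everything before the injection as safety baseline. SAP 6.8 then says "Preexisting conditions and adverse events (AEs) at baseline are those AEs occurring during the baseline/screening visits for the study period", and places these among patient characteristics, by preferred term within system organ class. Expulsion appears in the SAP only in Appendix 1, as a category of important deviation that concerns the check, not its result.

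**The concern.** The capsule is imposed by the study, and the first is swallowed about a week before the injection. A reader of the safety report would expect to learn how many capsules were confirmed as passed, and how many adverse events investigators put down to the capsule or its procedure. The planned tables answer neither question. For the first capsule, some events would be found only in a baseline table that mixes them with conditions present before the patient entered the study.

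At stake are the completeness and attribution of harm from a study procedure. There is a secondary interest: the trial explores whether a difference in mechanism contributes to gastrointestinal adverse events. A capsule not confirmed as expelled may be a device problem, a sign of slow transit or a recording problem, and a count by capsule and arm would help the reader tell these apart.

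**Working it through.** **1. The plan's own figures.** Protocol 10.1 says "Assuming within-group mean difference in CTT is about 4.2 hours with standard deviation of approximately 8", and that "a sample of 30 patients in each treatment group will provide 80% power to detect the difference within the treatment group". For a paired test at 2-sided 0.05, the standardised shift is (4.2/8) × √30 = 2.88. Power is 79.4% by the noncentral t and 82.0% by the normal approximation, so the stated 80% is reproduced. Screening: 60/(1 − 0.20) = 75, also reproduced. Neither figure bears on this point, except that 2 × 30 = 60 dosed patients sets the number of capsules.

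**2. Exposure.** 60 patients × 2 capsules = 120 planned ingestions. The first 60 precede the injection: 60/120 = 50%.

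**3. Where an event in a dosed patient is tabulated.**

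| Event | Planned location | Device or procedure attribution |
|---|---|---|
| Non-serious, onset between first capsule and injection, no worsening, no discontinuation | SAP 6.8 baseline summary only; not treatment-emergent (SAP 6.11.3), not in the registry Other category (SAP 6.16) | None |
| Same, but worse after injection | Treatment-emergent tables | None |
| Serious, at any time | SAE table (SAP 6.11.4) and registry SAE data (SAP 6.16), treatment-emergent or not | None |
| Leading to discontinuation | Its own table by preferred term (SAP 6.11), with no treatment-emergent limit stated | None |
| New or worse after the second capsule | Treatment-emergent tables by preferred term | None |
| Expulsion not confirmed, or x-ray taken, and not recorded as an adverse event | No planned summary | Not applicable |

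The first and last rows are the gaps in coverage. The empty right-hand column is the gap in attribution.

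**4. What a count by capsule would give.** With zero retentions, the exact upper limit of a two-sided 95% interval is 1 − 0.025^(1/n):

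- one capsule per patient, n = 60: 6.0%
- both capsules, n = 120: 3.0%, treating ingestions as independent, which two in the same patient are not strictly.

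The documents give no retention rate. If the risk per capsule were 0.1% to 2% (an assumption), the chance of at least one retention, 1 − (1 − p)^n, would be 6% to 70% in 60 capsules and 11% to 91% in 120. That range is too wide to support any claim about frequency.

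**The case against.** A reader might infer that the named device harm is misreported, or that first-capsule events are outside every adverse event table unless they worsen. The documents do not support either. Serious events are tabulated whenever they occur, events leading to discontinuation have their own table, and second-capsule events enter the treatment-emergent tables. The label in SAP 6.8 also covers adverse events at baseline, so lead-in events are not simply called preexisting.

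The lead-in route also fits retention less well than it fits symptoms. First-capsule expulsion is checked at Visit 3, and SAP 6.11.1 places dosing at the start of that visit, so a retention may be found and recorded after the injection.

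One might also infer that capsule events distort the drug comparison. Both randomised arms have the same capsule, fast and test meal, so no bias between arms is shown. Investigators know the treatment, so their relatedness judgements are themselves open to influence. This is a good reason to keep the treatment-emergent tables undivided and to treat any relatedness split as descriptive.

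Finally, the SAP section is about the tolerability of treatment, the capsule is a commercial measuring device, and Protocol 10.3.1 allows further exploratory analyses. The data are not lost. It is also not certain that the eCRF has a separate device field, or fields for expulsion and x-ray.

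All of this stands, and it limits the point. It does not close the two gaps in coverage, and none of the tables it cites gives attribution. The discontinuation table is also less of a safeguard than it looks. Protocol 8.1.1 makes retention or aspiration a reason to stop study treatment, but Protocol 7.2.1 gives treatment only once, at Visit 3, so nothing remains to stop after the second capsule. Those two passages need to be reconciled.

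**Conclusion.** The concern holds in a limited form. Capsule harm is not attributed to the device or procedure, and it is shown incompletely. The stated rules put one class of first-capsule event (non-serious, not worsening, not leading to discontinuation) under patient characteristics only, and the expulsion outcome is not reported at all. About half of the planned ingestions in dosed patients (60 of 120) fall in the period concerned.

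This rests on the planned 60 dosed patients each swallowing two capsules and on reading SAP 6.8, 6.11 and 6.16 as written. It makes no claim about how often such events occur. No primary or secondary conclusion of the trial changes. It is a worthwhile and inexpensive reporting improvement.

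**What to change.** Reporting changes only:

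- **SAP 6.11, relatedness.** Add adverse event summaries by relatedness to study procedure, and to study device if a separate field is captured, beside the existing one for treatment. Label them descriptive.
- **SAP 6.11, expulsion.** Add one table by capsule (first, second) and arm: number ingested, expulsion confirmed, x-ray obtained, expulsion not confirmed. Keep the last separate from retention, because a truncated recording can also leave expulsion unconfirmed.
- **SAP 6.8.** Limit preexisting conditions to onset before the first ingestion. Tabulate events from that ingestion to the injection as adverse events of a lead-in capsule period.
- **Unchanged.** Leave the treatment-emergent definition for the drug comparison as it is. Nothing here alters dosing, imaging or stopping rules.

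The cost is SAP wording, two or three descriptive tables, and a check of which relatedness, expulsion and x-ray fields exist. If a field is missing, the table that needs it has to be reduced or the field added. No extra visit, procedure or patient is needed. Counts will be small.

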### 6.11.1. Extent of Exposure

Patients will receive study treatment at the beginning of Visit 3.

The following information will be recorded on the eCRF for each dose:

- confirmation that the patient received study treatment (including reason if study treatment was not administered), and
- date and time of administration.

A listing of patient exposure will be produced.

### 6.11.2. Treatment Compliance

A by-patient listing of doses received will be generated, including dose date, number of injections, and location of injection.

### **6.11.3. Adverse Events**

Treatment-emergent AEs are defined as reported AEs that first occurred or worsened during the postbaseline phase compared with the baseline phase. For each TEAE, severity (mild, moderate, or severe) will be determined by patient or physician opinion. The Medical Dictionary for Regulatory Activities (MedDRA) lowest level term (LLT) will be used in the TE computation. For each LLT, the maximum severity at baseline will be used as the baseline severity. If the maximum postbaseline severity is greater than the maximum baseline severity, the event will be considered TE for the specific postbaseline period.

For each patient and TEAE, the maximum severity for the specified MedDRA level (PT, high level term, or SOC) will be the maximum postbaseline severity observed from all associated LLTs mapping to that MedDRA level.

For events that are gender specific, the denominator and computation of the percentage will include only patients from the specified gender.

### **6.11.4. Serious Adverse Events and Other Notable Adverse Events**

An SAE is any AE that results in one of the following outcomes:

- death
- initial or prolonged inpatient hospitalization
- a life-threatening experience (that is, immediate risk of death)
- persistent or significant disability/incapacity
- congenital anomaly/birth defect, or
- important medical events that may not be immediately life threatening or result in death or hospitalization but may jeopardize the patient or may require intervention to prevent one of the other outcomes listed in the definition. Examples of such medical events include allergic bronchospasm requiring intensive treatment in an emergency room or at home, blood dyscrasias or convulsions that do not result in inpatient hospitalization, or the development of drug dependency or drug abuse.
- When a condition related to the autoinjector (AI) pen necessitates medical or surgical intervention to preclude either permanent impairment of a body function or permanent damage to a body structure, the serious outcome of ‘required intervention’ will be assigned.

All SAEs will be summarized by PT.

### **6.11.5. Clinical Laboratory Evaluation**

Investigators are responsible for the appropriate medical care of patients during the study and must document their review of each laboratory safety report. Local urine pregnancy tests should be conducted according to the Schedule of Activities (see Section 2 of Protocol CGBC).

Pregnancy (during maternal or paternal exposure to study treatment) does not meet the definition of an AE.

No analyses of clinical laboratory evaluations will be produced.

#### **6.11.6. Vital Signs and Other Physical Findings**

Vital signs collected during the study include systolic (SBP) and diastolic blood pressure (DBP), pulse, and temperature. Blood pressure and pulse measurements will be taken when the patient is in a sitting position.

The number and percent of patients meeting criteria for categorical changes of interest in vital signs at any time during study will be summarized. Treatment group comparisons will be performed using Fisher's exact test.

[Table CGBC.6.1](#) displays the criteria for categorical changes of interest in vital signs. The last column of the table displays the patient populations defined by baseline categories.

The criteria to identify patients with TE abnormal changes generally consist of 2 parts: an absolute threshold and a change from baseline amount.

- The absolute threshold in the criteria is based on 1) minimum postbaseline when the direction is low; 2) maximum postbaseline when the direction is high.
- The change from baseline amount in the criteria is 1) decrease from baseline to minimum postbaseline when the direction is low, and 2) increase from baseline to maximum postbaseline when the direction is high.

The baseline for SBP, DBP, pulse, and temperature is defined as the last non-missing baseline value during the baseline period. This baseline definition for SBP, DBP, pulse, and temperature applies to all analyses (both continuous and categorical) for SBP, DBP, pulse, and temperature.

Any clinically significant finding from vital sign measurements that results in a diagnosis and that occurs after the patient receives the first dose of study treatment should be reported as an AE via eCRF to Eli Lilly and Company or its designee.

Other physical findings will be collected at Visit 1. No analyses of other physical findings will be produced.

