Appendix 2.4. Publication Policy

The publication policy for Study I5Q-MC-CGBC is described in the Clinical Trial Agreement.

**Appendix 3. Protocol Amendment
I5Q-MC-CGBC(a) Summary
A Phase 4 Single-Blind Study of Gastrointestinal Transit
Time in Adult Patients with Migraine Before and After
Initiation of a mAb CGRP Antagonist**

Overview

Protocol I5Q-MC-CGBC(a) A Phase 4 Single-Blind Study of Gastrointestinal Transit Time in Adult Patients with Migraine Before and After Initiation of a mAb CGRP Antagonist has been amended. The new protocol is indicated by amendment (a) and will be used to conduct the study in place of any preceding version of the protocol.

The overall changes and rationale for the changes made to this protocol are described in the following table:

Amendment Summary for Protocol I5Q-MC-CGBC Amendment (a)

Section # and Name	Description of Change	Brief Rationale
Global	The study has been amended from an open-label study to a single-blind study.	This change was made to reduce potential for patient bias, as the frequency and consequences of constipation for erenumab and galcanezumab are not the same based on a recent USPI update for erenumab regarding constipation.
	Minor editorial changes	Minor editorial changes were made to improve clarity.
Title	CGRP Antagonist has been clarified to mAb CGRP Antagonist.	This clarification was made due to the recent approval of oral CGRP antagonists.
Section 2 Schedule of Activities	Vital sign assessments have been added to Visits 3, 4, and 5.	The additional vital sign assessments were added due to the April 2020 update to the erenumab USPI with Warning and Precautions language for new-onset or worsening of pre-existing hypertension based on postmarketing information.
Section 6.1 Inclusion Criteria	Chronic migraine has been removed from Inclusion Criterion [2].	The chronic migraine diagnosis was removed because this patient population has a higher frequency of headaches per month, which can be associated with more comorbidity. Therefore, this change was made to reduce variation in the population due to the small sample size and the exploratory nature of the study. Chronic migraine was also removed from Inclusion Criterion [4] due to this change.

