**Table CGBC.6.1. Criteria for Categorical Changes of Interest in Vital Signs**

Parameter	Direction	Criteria	Patient Population defined by Baseline Categories
Systolic BP (mm Hg) (sitting)	Low	$\leq 90$ and decrease $\geq 20$	All patients; $>90$ ; $\leq 90$
	High	$\geq 140$ and increase $\geq 20$	All patients; $<140$ ; $\geq 140$
	PCS High	$\geq 180$ and increase $\geq 20$	All patients; $<180$ ; $\geq 180$
	Sustained Elevation	$\geq 140$ and increase $\geq 20$ at 2 consecutive visits	All patients; $< 140$ ; $\geq 140$
Diastolic BP (mm Hg) (sitting)	Low	$\leq 50$ and decrease $\geq 10$	All patients; $>50$ ; $\leq 50$
	High	$\geq 90$ and increase $\geq 10$	All patients; $<90$ ; $\geq 90$
	PCS High	$\geq 105$ and increase $\geq 15$	All patients; $<105$ ; $\geq 105$
	Sustained Elevation	$\geq 90$ and increase $\geq 10$ at 2 consecutive visits	All patients; $< 90$ ; $\geq 90$
Systolic BP or Diastolic BP (mm Hg) (sitting)	Sustained Elevation	Meeting criteria for systolic BP for 2 consecutive visits or meeting criteria for diastolic BP for 2 consecutive visits or both	All patients
Pulse (bpm) (sitting)	Low	$<50$ and decrease $\geq 15$	All patients; $\geq 50$ ; $<50$
	High	$>100$ and increase $\geq 15$	All patients; $\leq 100$ ; $>100$
	Sustained Elevation	$>100$ and increase $\geq 15$ at 2 consecutive visits	All patients; $\leq 100$ ; $>100$
Temperature ( $^{\circ}$ F)	Low	$<96^{\circ}$ F and decrease $\geq 2^{\circ}$ F	$\geq 96^{\circ}$ F
	High	$\geq 101^{\circ}$ F and increase $\geq 2^{\circ}$ F	$<101^{\circ}$ F

Abbreviations: BP = blood pressure; PCS = potentially clinically significant.

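### Post-dose blood pressure was added because of a hypertension warning, but the only comparison the SAP specifies for it is Fisher's test on threshold counts; the continuous analysis it alludes to is never defined

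*SAP*

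**What the plan says.** The Protocol's Schedule of Activities places vital signs at Visits 1, 3, 4 and 5; its note reads "Includes body temperature, sitting blood pressure, and pulse". The amendment summary (Protocol Appendix 3) attributes the additions at Visits 3, 4 and 5 to an update of the erenumab "USPI with Warning and Precautions language for new-onset or worsening of pre-existing hypertension based on postmarketing information". Protocol 3.3 states the same risk: "new-onset or worsening of pre-existing hypertension have been reported with erenumab in postmarketing experience".

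The SAP revision history records that vital-sign analyses were introduced in version 2. SAP 6.11.6 describes them: "The number and percent of patients meeting criteria for categorical changes of interest in vital signs at any time during study will be summarized". It continues: "Treatment group comparisons will be performed using Fisher's exact test". The criteria are in Table CGBC.6.1, "Criteria for Categorical Changes of Interest in Vital Signs". For example, systolic High needs a maximum post-baseline value of at least 140 mmHg together with a rise of at least 20; diastolic High needs at least 90 with a rise of at least 10. Sustained Elevation needs the criterion at two consecutive visits.

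Baseline is the last non-missing pre-dose value, and 6.11.6 says that this definition "applies to all analyses (both continuous and categorical) for SBP, DBP, pulse, and temperature". No continuous analysis of post-baseline vital signs follows. The ANOVA in SAP 6.11 is for demographics and baseline characteristics, and the MMRM in SAP 6.10.2 is for efficacy measures.

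**The concern.** The readings were added to look at one named risk. Reducing each patient's readings to a yes/no crossing discards most of the information about a general rise, and Fisher's test on rare events in two groups of 30 is very insensitive. The continuous analysis that would use the readings fully is implied but undefined, so it could be omitted or chosen after the data are seen. A table of non-significant Fisher p-values would not tell a reader how large a rise the trial could or could not exclude.

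**Working it through.** **Inputs from the documents.** 30 patients per arm, 1:1 (Protocol 10.1, SAP 5.2); two-sided alpha 0.05 (SAP 6.5); criteria from Table CGBC.6.1. Taking the Visit 3 reading as pre-dose, Visits 4 and 5 are the only post-dose readings.

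**The plan's own figure.** The documents make no power claim for blood pressure. The 30 per arm comes from colonic transit time: (8 × (1.960 + 0.842) / 4.2)² = 28.5. At n = 30 the power is 82% by the normal approximation and 79% by the noncentral t, so the stated 80% reproduces.

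**Step 1: Fisher's test at 30 v 30, with no blood-pressure assumptions.**

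| Events | p |
|---|---|
| 5 v 0 | 0.052 |
| 6 v 0 | 0.024 |
| 7 v 1 | 0.052 |
| 8 v 1 | 0.026 |
| 9 v 2 | 0.042 |

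Exact power by binomial enumeration is 4% for true crossing rates of 2% v 10%, 9% for 5% v 15%, and 24% for 5% v 20%.

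**Step 2: the same readings analysed as means.** The assumptions, none of them in the documents, are: systolic mean 118; baseline SD 12 including visit noise; visit-to-visit SD 8; between-patient SD of change 5; normal and independent errors; no dropout; no shift in the other arm.

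- Variance of patients' true levels: 12² − 8² = 80.
- Change score, mean of Visits 4 and 5 minus one baseline reading: 5² + 8²/2 + 8² = 121, so SD 11.0.
- Baseline-adjusted: the variance of the two-visit mean is 80 + 25 + 32 = 137; the residual variance is 137 − 80²/144 = 92.6, so SD 9.6.
- Standard error of the arm difference: SD × √(2/30), which is 2.84 and 2.48 mmHg.
- At +6 mmHg the noncentralities are 6/2.84 = 2.11 and 6/2.48 = 2.42, so the power is 55% and 66%.
- Simulating the same model, systolic High rises from 2.5% to 7.9% of patients, and Fisher power is about 1%.

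**Step 3: range.** The second set of settings assumes mean 120, SD of patients' true levels 10, visit SD 6 to 10 and no between-patient variation in change.

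| Setting | Systolic shift | Fisher, High | Change score | Baseline-adjusted |
|---|---|---|---|---|
| Step 2 values | +3 | 0.1% | 18% | 22% |
| Step 2 values | +6 | 1% | 55% | 66% |
| Step 2 values | +10 | 16% | 93% | 98% |
| Second set | +3 | 0–0.6% | 15–34% | 21–40% |
| Second set | +5 | 0–2% | 34–74% | 48–81% |
| Second set | +10 | 3–25% | 87 to >99% | 97 to >99% |
| Mean 128, SD 12, visit SD 8 | +10 | 35% | 97% | 99% |

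For diastolic pressure (mean 76, SD 7, visit SD 4 to 8), a +5 shift gives Fisher 3–15% against 69–99% baseline-adjusted. Fisher on Sustained Elevation is at 0.5% or less in every setting of the second and third kinds and in the diastolic ones, because both Visits 4 and 5 must qualify.

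**Step 4: precision of a mean difference.** The 95% half-width is 2.002 × SD × √(2/30): 4.1, 5.2 and 6.2 mmHg at SD 8, 10 and 12.

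**The case against.** **Continuous analysis is not excluded.** A reader might infer that the sponsor chose to analyse blood pressure as counts alone. The reference to continuous analyses in 6.11.6 speaks against that, and the general MMRM wording in SAP 6.2 could be stretched to cover vital signs. This stands as a limit on the point: the defect is an unspecified analysis, not a rejected one. It does not close the gap, because nothing links the 6.2 model to blood pressure.

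**Adverse events are a second route.** A clinically significant vital-sign finding that leads to a diagnosis is reported as an adverse event, so hypertension can also appear in the TEAE tables. This is correct. Those summaries still do not estimate a shift in pressure.

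**Counts suit the labelled risk.** Postmarketing reports of new or worsening hypertension concern individual patients, and counts are a sensible screen for a few large responders. This also stands, and is why the counts should be kept.

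**The effect sizes are outside assumptions.** The documents give no blood-pressure mean, SD or expected shift. A reader might therefore conclude too readily that Fisher has no chance and that a mean comparison would settle the matter. Neither follows: at +3 mmHg the mean comparison is weak too, and at +10 mmHg Fisher's power is no longer negligible. It is also easy to overstate the comparator by treating the baseline reading as error-free. That gives a change SD of √(5² + 8²) = 9.4 and power at +6 mmHg of 68% (one visit) or 86% (two visits). With baseline noise included, the change-score figures are 46% and 55%.

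**Blood pressure is safety monitoring in a transit study.** The documents state no blood-pressure hypothesis and promise no conclusion of no effect, so misreading of the table is a risk and not a stated intention.

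**Conclusion.** The point holds as a gap in specification with a practical cost. The measurements were added for a hypertension signal; the one specified comparison needs at least 6 v 0 or 8 v 1 to reach significance; and the continuous analysis mentioned is not defined. Those facts rest on the documents and exact arithmetic alone.

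The contrast in power rests on assumed blood-pressure values. For a general systolic rise of about 5 to 6 mmHg it is roughly 0–2% for Fisher against 34–81% for a comparison of means. The direction is the same in every setting tried, but the exact figures are not firm. The documents do not support saying that continuous analysis was ruled out, that hypertension could be seen only in the threshold table, or that Fisher's test could never detect a rise. The change should be made, but it does not touch the primary analysis.

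**What to change.** In SAP 6.11.6, specify change from baseline in systolic pressure, diastolic pressure and pulse at Visits 4 and 5, using the MMRM form already in SAP 6.2 with baseline and baseline-by-week terms. Report the LS mean change in each arm and the arm difference with 95% confidence intervals, by visit and averaged over the two visits. For systolic pressure the interval for the difference would be about ±4 to 6 mmHg at SD 8 to 12, which tells the reader what the trial can exclude.

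Keep the Table CGBC.6.1 counts alongside, since they address individual large responders, and label them and their Fisher p-values descriptive.

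The cost is one additional table. No new data are collected and the visit schedule does not change.
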